## LIST OF ABBREVIATIONS

AE	Adverse Event
AR	Adverse Reaction
CI	Cochlear Implant
CRF	Case Report Form
CRO	Contract Research Organisation
DMC	Data Monitoring Committee
ENT	Ear, Nose and Throat
GAfREC	Governance Arrangement for NHS Research Ethics
HA	Hearing Aid
HTA	Human Tissue Authority
IB	Investigator Brochure
ICF	Informed Consent Form
iSS	Infratentorial Superficial Siderosis
MD	Medical Device
ISRCTN	International Standard Randomised Controlled Studies Number
NHNN	National Hospital for Neurology and Neurosurgery
PI	Principle Investigator
PIS	Participant Information Sheet
QA	Quality Assurance
QC	Quality Control
RCT	Randomised Clinical Study
REC	Research Ethics committee
RNTNEH	Royal National Throat Nose and Ear Hospital
SAR	Serious Adverse Reaction
SAE	Serious Adverse Event
SDV	Source Data Verification
SOP	Standard Operating Procedure
SSI	Site Specific Information
TMF	Trial Master File

## STUDY SUMMARY

Study Title	CLINICAL AND IMAGING BIOMARKERS OF AUDIO-VESTIBULAR FUNCTION IN INFRATENTORIAL SUPERFICIAL SIDEROSIS
Internal ref. no. (or short title)	Audiovestibular function in infratentorial superficial siderosis (AViSS)
Study Design	Observational study
Study Participants	
 
1) Siderosis group: participants with known diagnosis of infratentorial superficial siderosis;
 
2) Age-related hearing loss group: participants with known age-related hearing loss;
 
3) Control group: participants with no known or previously reported hearing loss;
 

Planned Size of Sample (if applicable)	60-90 participants in total: 20-30 participants - siderosis group 20-30 participants - age-related hearing loss group 20-30 participants - control group
Follow up duration (if applicable)	12 months
Planned Study Period	3 years
Research Question/Aim(s)	
 
(1) To systematically review the literature on audiovestibular function in iSS including most up-to-date available treatment options
 
(2) To comprehensively assess the profile of audiological and vestibular dysfunction in iSS including its impact on the quality of life in comparison to that of age-related hearing loss and the control groups (hearing function) and normative data (balance/vestibular function);
 
(3) To correlate the pattern and degree of hearing loss and vestibular dysfunction in iSS with the imaging findings and other clinical parameters;
 

## ROLE OF STUDY FUNDER

NIHR UCLH BRC does not control the final decision regarding study design, conduct, data analysis and interpretation, manuscript writing, and dissemination of results.

## **ROLES AND RESPONSIBILITIES OF STUDY MANAGEMENT COMMITTEES /GROUPS & INDIVIDUALS**

### **Study Steering Groups**

The Chief Investigator (CI) and secondary academic supervisors (study co-investigators) act as a study steering group for study coordination and conduct.

**SPONSOR:** The sponsor is responsible for ensuring before a study begins that arrangements are in place for the research team to access resources and support to deliver the research as proposed and allocate responsibilities for the management, monitoring and reporting of the research. The Sponsor also has to be satisfied there is agreement on appropriate arrangements to record, report and review significant developments as the research proceeds, and approve any modifications to the design.

**FUNDER:** The funder is the entity that will provide the funds (financial support) for the conduction of the study. Funders are expected to provide assistance to any enquiry, audit or investigation related to the funded work.

**CHIEF INVESTIGATOR (CI):** The person who takes overall responsibility for the design, conduct and reporting of a study. If the study involves researchers at more than one site, the CI takes on the primary responsibility whether or not he/she is an investigator at any particular site.

The CI role is to complete and to ensure that all relevant regulatory approvals are in place before the study begins. Ensure arrangements are in place for good study conduct, robust monitoring and reporting, including prompt reporting of incidents, this includes putting in place adequate training for study staff to conduct the study as per the protocol and relevant standards.

The CI is responsible for submission of annual reports as required. The Chief Investigator will notify the RE of the end of the study, including the reasons for the premature termination. Within one year after the end of study, the Chief Investigator will submit a final report with the results, including any publications/abstracts to the REC.

**PRINCIPLE INVESTIGATOR (PI):** Individually or as leader of the researchers at a site; ensuring that the study is conducted as per the approved study protocol, and report/notify the relevant parties – this includes the CI of any breaches or incidents related to the study.

[figure not shown]
**RESEARCH STUDENT/STUDY CO-ORDINATOR:** the person who carries out the research study, including: (1) identifying suitability of potential participants to take part in the study, (3) obtaining formal consent from the participants, (2) arranging participants visits, (4) carrying out the assessments and procedures outlined in the protocol, (5) collecting and analysing the data, (6) results write-up and (7) dissemination.

**ACADEMIC CO-SUPERVISOR:** the person who contributes to the study conception, including the scientific rationale, as well as design, study methodology, feasibility, conduct, reporting of the study and supervises the research student and his/hers research activity.

**KEY WORDS:**

- Superficial siderosis, infratentorial
- Nervous system diseases
- Auditory pathways
- Hearing tests
- Vestibulocochlear nerve
- Vestibular function tests
- Hearing loss
- Ataxia
- Biomarkers

## STUDY FLOW CHART

\*Infratentorial Superficial Siderosis (iSS)

\*\*Age-related Hearing Loss (ARHL)

## **STUDY PROTOCOL**

### **1. BACKGROUND**

One in six people in the UK, and over 400 million people worldwide according to the World Health Organisation have disabling hearing loss. These figures are predicted to increase to over 600 and 900 million by 2030 and 2050 respectively (1). However, our understanding of progressive hearing loss is limited and remains the focus for worldwide research.

The current widely accepted and most commonly used method of hearing assessment remains to be pure tone audiometry (PTA). There is, however, a growing body of evidence that PTA is not reflective of true hearing impairment, as it is not representative of the function of the entire auditory pathway (2). The audiological tests (or their combination) that best characterise the overall and disease-specific hearing loss are yet to be determined. The use of speech in noise tests has been previously recognised as a more accurate measure of hearing as it best resembles hearing function in day-to-day life. Speech in noise tests however are not routinely used in the clinical setting. In addition, two most common maskers (types of background noise) used in the speech in noise tests are steady-state speech and background babble. The latter has been demonstrated to be a more sensitive marker of changes in speech discrimination ability and has more face validity, as these testing conditions more realistically resemble real life-situations (3-5).

In the face of increasing prevalence of hearing impairment, there is an urgent need to improve our knowledge regarding hearing loss, its underlying mechanisms, diagnostic methodology, preventative and rehabilitative measures. Together with that comes the need to identify optimal functional and imaging biomarkers and tests that can accurately and reliably identify the site-of-lesion and measure hearing dysfunction.

While our scientific knowledge of the major factors responsible for this increase in the prevalence of hearing loss (both noise-induced and age-related hearing loss, ARHL) is rapidly expanding, our understanding of several less frequent causes of hearing loss of progressive nature remains limited (1).

---

 WHO define disabling hearing loss as hearing loss greater than 40dB in the better hearing ear (adults) and greater than 30dB in the better hearing ear (children)

Superficial siderosis (infratentorial, iSS) is one such condition implicated in progressive disabling hearing loss. It arises from deposition of iron along the surfaces of the brain and spinal cord (6-8). Chronic or repetitive leak of blood into the subarachnoid space leads to accumulation of iron in the sub-pial layers and subsequent neuronal loss, gliosis and demyelination (7, 8). It has been considered uncommon until the advent of Magnetic Resonance Imaging (MRI) which has contributed to increased diagnoses of iSS (9).

The prevalence of superficial siderosis of the CNS has been compared to that of multiple sclerosis, with the respective figures reported at 0.15 and 0.19 percent (10-12) and reported at 0.56 and at 0.7 percent in population-based studies from Minnesota by Pichler et al and the Netherlands by Vernooij et al (cortical superficial siderosis) (13, 14). The prevalence of superficial siderosis in the UK is currently unknown.

Two types of haemosiderosis within the CNS are recognised: supratentorial (cortical) and infratentorial. Both constitute distinct entities and differ in their clinical, radiological and pathophysiological characteristics, although both patterns have been reported to co-exist (7, 15, 16). In cortical (supratentorial) superficial siderosis (cSS), which is often associated with cerebral amyloid angiopathy, the haemosiderin deposits are distributed in the supratentorial pattern and are limited to the cerebral hemispheres (16-18). Hearing impairment or symptoms of imbalance or ataxia are rarely reported in this group.

In contrast, infratentorial superficial siderosis (iSS) is characterised by progressive (often moderate-to-severe) sensorineural hearing loss (SNHL), poor balance and anosmia (8). The infratentorial structures such as cerebellum, brainstem and vestibulocochlear nerve appear to be most susceptible to haemosiderin deposits resulting in the clinical presentation of auditory and balance dysfunction (6-8, 19). Although it can occur at any age, it has frequently been reported in middle-to-older age patients (8, 20). This is likely to be due to its insidious onset and protracted course (often lasting decades), which can contribute to late diagnosis, and significant morbidity may be established by then (8, 10, 11).

Currently, studies that provide comprehensive analyses of auditory and vestibular function in iSS are few. Our knowledge regarding the impact of iSS on the audio-vestibular function is limited to case reports and case series, with patient numbers reported mainly in single figures. The largest two studies to date are by Sydlowski et al and Takeda et al, comprising of ten participants in each,

focusing on audiological and vestibular findings (10, 21, 22). The largest cohort of patients with iSS with hearing loss and ataxia symptoms was reported by Wilson et al from the National Hospital for Neurology and Neurosurgery (NHNN), London, which included 65 patients (7). This, however, was in part a retrospective study focusing on imaging findings, aetiology and diagnostic pathway of assessment. The information on audiovestibular symptoms was obtained from the medical records and it is likely that audiovestibular dysfunction was under-ascertained in this cohort.

In the literature that is available, there appears a lack of uniformity in the audiological and vestibular assessments of patients with iSS. The majority of reports describe the findings of pure tone audiometry (PTA) and characterise the hearing loss as bilateral sensorineural, which can be asymmetric and of variable degree – from mild to moderate to profound – usually with sparing of lower frequencies (8, 10, 21, 23, 24). These reports liken the pattern of hearing loss in iSS to age-related hearing loss (ARHL), when compared on the basis of pure-tone audiogram (10, 25).

Some studies and case reports have included findings of auditory brainstem evoked responses (ABRs) (8, 25-32) as well as speech audiometry (23, 26, 31, 33-36), acoustic reflexes (8, 27, 29), oto-acoustic emissions (OAE) (27-29, 33, 35), and electrocochleography testing (ECoG) (25, 34). In these, hearing loss is reported to be predominantly of retro-cochlear origin, with variable stapedial reflexes and ABR findings (8, 21, 27, 29).

The reports of balance assessment in iSS appear to be fewer, compared to the volume (albeit small) of the audiological reports (22). Where such reports are available, the vestibular test battery is not fully described nor appears to be uniform. While a few studies report on electronystagmography (ENG) findings (23, 27, 30), some also describe vestibular evoked myogenic potential (VEMP) (37) testing and video head impulse testing (v-HIT) (28, 38, 39). The reports describe mixed vestibular dysfunction – with both central and peripheral involvement (30, 40, 41).

In addition to the audiological and vestibular dysfunction associated with iSS, cognitive impairment has also been reported as one of the myriad symptoms associated with iSS (8, 42) yet few dedicated studies provide detailed assessment (29, 43). In a dedicated case series of six patients, van Harskamp et al identified deficits in speech production, executive functioning and visual recall

memory (29), whereas deficits in other cognitive domains have also been described in a number of case reports (43-45).

Greater availability and accessibility of MR imaging has resulted in more frequent recognition of the radiological features of iSS: hypo-attenuating rims along the surfaces of the brain, brainstem, and spinal cord in close proximity to the CSF, including the cerebellar folia, and along the vestibulocochlear nerves (7, 9, 46). MRI brain (and often MRI spine) has now become the modality of choice to investigate ataxia and SNHL in patients in whom the diagnosis of iSS is suspected (7, 9, 46). Computerised tomography (CT) has been shown to be less sensitive and less specific than MRI (8, 46).

Despite the increased recognition and detection of iSS on MRI, close correlation of radiological findings and audiovestibular function in patients with iSS, has not been previously reported. No radiological studies to date have attempted to localise the affected segment of the audiological and vestibular pathways or to correlate the audiovestibular dysfunction with the findings on imaging.

The diagnosis of iSS and the presence of active bleeding into the cerebrospinal fluid (CSF) can be confirmed by examining CSF for iron degradation products and the presence of red blood cells. Some patients exhibit heavy loads of these components on CSF analysis. It is not yet established whether these would correlate with symptom load.

The current treatment of iSS centres on removing the source of bleeding through a number of mechanisms, including ablation of the culprit vessel, repair of dural defect or excision of the offending lesion (42, 47, 48). The non-surgical treatment may include use of iron-chelating agents such as Deferiprone and its use in siderosis patients has demonstrated some degree of improvement in balance symptoms as well as radiological features on longitudinal imaging studies (49, 50). The use of deferiprone, however, has also been linked with the risk of agranulocytosis and neutropenia (8, 46, 47, 51, 52).

Hearing improvement measures for patients with iSS have been limited to conventional hearing aiding and hearing rehabilitation. Cochlear implantation (CI) in iSS patients has been previously described, yet mixed results were reported regarding its benefit (33, 53-55).

In summary, our knowledge of the impact of iSS on audiovestibular and other functions is limited. Specifically, the diagnostic value of the current battery of audiovestibular tests and their correlation with the radiological findings and other clinical parameters in iSS, including CSF results, in iSS needs to be determined. In addition, it remains to be determined what audiological tests or their combination would best characterise hearing impairment in iSS when compared to individuals with no previous history of hearing loss and to the individuals with age-related pattern of hearing loss. Thus, further studies with larger patient cohorts with iSS as well as studies that employ comprehensive battery of audiological tests and imaging and other clinical tests are needed to reliably identify and quantify hearing dysfunction and its mechanism in iSS.

## 2. RATIONALE

Presence of progressive and disabling sensorineural hearing loss (SNHL), imbalance and ataxia are the most common clinical features associated with iSS (8). Yet few reports in the literature provide a detailed description of these characteristics. We hypothesise that due to limited knowledge, iSS is likely to be under-recognised in the clinical setting, and thus under-diagnosed and under-reported. Further studies with larger patient cohorts and comprehensive battery of audiological and vestibular tests are required to gain greater understanding and knowledge regarding functional deficits in iSS.

Literature reports describe the pattern of hearing loss in iSS on pure-tone audiometry (PTA), to be similar to age-related hearing loss (ARHL) – down-sloping pattern with the initial loss at higher frequencies. What differentiates the auditory impairment in iSS, is the asymmetrical pattern and earlier onset of hearing loss than expected for ARHL(10). Similarities of pattern of hearing impairment between iSS and ARHL are likely to lead to iSS being misdiagnosed, and may result in disease progression and delayed diagnosis. When assessing the auditory function in iSS with ABR, speech audiometry and stapedial reflex testing, the literature suggests that hearing loss is of retro-cochlear origin.

Due to the lack of reports of comprehensive audiological assessment, the distinct pattern of hearing impairment in iSS patients remains to be elucidated. We hypothesise that the audiological profile of patients with iSS differs from that of individuals with ARHL and that a specific and pathognomonic audiological pattern attributable to iSS may exist. We further hypothesise that pure tone audiometry alone cannot reliably characterise the hearing dysfunction in iSS and that the use of extended audiometric battery of tests is needed to identify the precise audiological deficits in iSS.

We also hypothesise that there will be a greater deficit in speech-in-noise tests in iSS group compared with the ARHL and the control groups, when controlling for hearing deficits and that the speech-in-noise tests are better predictors of hearing dysfunction in iSS than PTA alone or with speech-in-quiet testing. We thus anticipate that speech-in noise tests will account for greater auditory deficits and will better correlate with patient-reported auditory difficulties than PTA and speech-in-quiet tests. We also anticipate a words-in-background babble test will be more able to predict auditory and cognitive impairment in iSS patients than a words-in-background speech noise.

Due to limited volume of literature that describes vestibular function in iSS and its heterogeneity in the battery of tests used, there is a need to provide a comprehensive description of vestibular function in these patients. We hypothesise that balance dysfunction will be due to a mixed (peripheral and central) vestibular deficits and that there will be a greater number of central and oculo-motor abnormalities detected in iSS patients when compared to normative data (40, 41). We also hypothesise that audiovestibular dysfunction will be identified in the majority of iSS patients after the initial radiological diagnosis and that these deficits will correspond to the involved structures of the auditory and vestibular pathways as visualised on brain images. Correlating the findings of assessments performed with the brain imaging would increase our understanding of the role of imaging in identification of the involved structure(s) of the audiovestibular pathways in iSS. Additionally, other clinical parameters may also be reflective of the symptom load or the degree of audiovestibular dysfunction and disease progression, and we would like to correlate the results of clinical tests performed in the clinical setting, including MRI, with the audiovestibular findings.

It is likely that iSS and its associated progressive and debilitating hearing and balance impairment) have a negative impact on quality of life. To our knowledge, this has not been reported in the literature and further studies are required to determine this. We will therefore assess the impact of iSS on the quality of life in patients with iSS.

Additionally, 20 percent of iSS patients were reported to have cognitive impairment by Kumar et al yet literature reports of cognitive assessment in iSS are few (56). The cognitive dysfunction may be specific to iSS or due to progressive hearing impairment or a combination of both, and further studies are required establish this. Similarly to cognitive function, olfaction has been reported to affect patients with iSS in 17 percent of patients, yet is rarely reported in the literature (8). We therefore will assess the olfactory function and will use (University of Pennsylvania) Smell Identification Test (SIT).

We further hypothesise that there is a genetic predisposition to the development of iSS which may contribute to the degree of associated symptoms. We will collect the saliva samples from the iSS participants (self-collected) to biobank the DNA for genetic analysis during this study or for use in other or future studies.

As part of this study we will collect self-report measures, such as Modified Amsterdam Inventory for Auditory Disability and Handicap (mAIDAH), Speech, Spatial and Qualities of Hearing Scale (SSQ) questionnaire and Tinnitus Functional Index (TFI) adjunct the auditory tests, and Dizziness Handicap Inventory (DHI) and Situational Vertigo Questionnaire (SVQ) alongside the vestibular tests. We hypothesise that these will reflect symptom load and may reflect functional deficits (as

identified on auditory, vestibular and cognitive tests), and we will correlate these with disease severity and the degree of functional impairment.

Because iSS is characterised by auditory and vestibular dysfunction which are reported to be disabling and debilitating it is also important to assess this over time. We hypothesise that the use of interval hearing and balance (vestibular) questionnaires in iSS participants may reflect changes in these functions, which may also be reflective in the quality-of-life questionnaires in these participants, and thus these can be used as a functional outcome measure to monitor disease progression and in the future research and clinical settings – to monitor response to treatment. We hypothesise that these can be used as an adjunct measure of degree of dysfunction and iSS progression than the currently available techniques, including imaging (57).

This will be one of the largest studies to date focusing on functional deficits in iSS, and will provide a detailed phenotype of its audiological and vestibular functions. The comprehensive test battery will allow to determine the accurate and disease-specific pattern of hearing and balance impairment in iSS. This in turn may lead to iSS being more frequently recognised, promptly diagnosed and timely initiation of treatment. In this study we will attempt to identify the tests that best measure functional impairment in iSS and can thus be used to assess the severity, and as a means of monitoring disease progression and the response to treatment. In addition, the study results will inform us regarding the most suitable and likely beneficial rehabilitative measures that can be offered to symptomatic patients with iSS in the clinical practice in the future.

This project will thus enhance our overall understanding and knowledge of hearing loss and imbalance, cognitive and olfactory functions in patients with iSS. By involving a larger cohort of patients which has previously been described by Wilson et al (7), we will be able to draw similarities with the reports evidenced in the literature and compare the findings to those of the age-matched individuals with ARHL and the control groups in the study. In addition, the use of comprehensive battery of hearing tests between the groups will help to determine tests that best identify and quantify auditory dysfunction. We will also be able to compare the results to the normative data and attempt to establish the impact of iSS on quality of life in comparison to individuals with age-related hearing loss and control group. This study will contribute to the global pool of knowledge regarding iSS and may improve understanding of this condition. This in turn may help inform research regarding means of diagnosis, management and rehabilitative measures, and monitoring of disease progression and treatment responses of audiovestibular dysfunction in iSS patients.

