## 4.2 Outcome questions

Primary outcome question: What are the salient and disease-specific features of auditory and vestibular dysfunction and what is the impact of iSS on olfactory and cognitive functions and on the quality of life?

Secondary outcome question: How do the imaging findings correlate with the results of audiological, cognitive and vestibular assessments and severity of symptoms?

Tertiary outcome question: Which audiological tests are able to better predict auditory impairment in iSS group compared to the ARHL and the control groups?

Quaternary outcome question: Can a combination of auditory testing approaches be used as a valid functional tool for hearing assessment and site of lesion testing in patients with auditory dysfunction based on the findings of the cohorts included in this study?

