6. *Speech-in-noise testing*: a set of tests with background noise/speech/babble, administered using appropriate programme through headphones, where words/sentences/speech presented in competing background noise/speech/babble (50-60mins)
7. *Functional Gait Assessment (FGA)*: assessment of postural stability; 10-point test, incorporating (head) turns, gait changes (that would usually include speed, narrow base, stairs, backwards, level, obstacles) (10mins)
8. *Scale for Assessment and Rating of Ataxia (SARA)*: clinical scale to assess cerebellar ataxia which is made up of 8 items related to gait, stance, sitting, speech, finger-chase test, nose-finger test, fast alternating movements and heel-shin test (15mins)
9. *Olfactory (smell) Smell Identification Test (SIT)*: self-administered test, a booklet with odour-impregnated pages; the odour is introduced to the tester by scratching the test booklets (10mins)
10. *Saliva sampling* for DNA biobanking (max 30ml, equivalent of the volume of maximum two table-spoons) (5mins)

11. *Hearing questionnaires* (which can be distributed to the participant ahead of the appointment and collected during their visit, after having given formal consent to participate in the study, as a time saving measure)

- *Modified Amsterdam Inventory for Auditory Disability and Handicap (mAIDH) questionnaire*: a 28-point self-report questionnaire that assesses listening ability on 5 domains (5mins)
- *Speech, Spatial and Qualities of Hearing Scale (SSQ) questionnaire*; contains 50 items and involves 3 hearing domains, namely: speech, spatial and qualities (of sound segregation and identification) (5mins)
- *Tinnitus Functional Index (TFI) questionnaire*; 25-item self-report questionnaire; has been shown to have higher validity than other tinnitus questionnaires (5mins)

12. *Vestibular questionnaires* (which can be distributed to the participant ahead of the appointment and collected during their visit, after having given formal consent to participate in the study, as a time saving measure) and will include:

- *Dizziness Handicap Inventory (DHI)*: self-report questionnaire on perceived impact of dizziness on daily life assessing (5mins)
- *Situational Vertigo Questionnaire (SVQ)*: self-report 19-item questionnaire that measures frequency of symptoms of disorientation/vertigo against visually busy environment (5mins)

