## 5.5 Data analysis methods

Quantitative Analysis will be conducted using dedicated statistical software package.

Statistical analysis will be performed under the guidance and with advice of a designated biostatistician at UCL and/or at Biostatistics Office, UCL(H) Joint Research Office (JRO).

Each variable will be checked for distribution skewness, and regression models for each variable will be constructed. For binary variables, chi-square tests will be performed in order to determine the difference in the findings between the siderosis group and the control groups.

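### The plan claims that speech-in-noise tests predict better than pure tone audiometry but contains no analysis that compares predictors, and leaves both scores and the self-report criterion open

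*Combined protocol and SAP*

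**What the plan says.** The claim is comparative. Section 2 states that "the speech-in-noise tests are better predictors of hearing dysfunction in iSS than PTA alone or with speech-in-quiet testing", and expects that speech-in-noise tests "will better correlate with patient-reported auditory difficulties than PTA and speech-in-quiet tests". Section 4.2 asks, as the tertiary outcome question, "Which audiological tests are able to better predict auditory impairment in iSS group compared to the ARHL and the control groups".

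The analysis text is short. In section 5.5 each variable is checked for skewness, "regression models for each variable will be constructed", and binary variables are compared between groups by chi-square. It gives no comparison of two correlations or two models, no measure of what 'better' means and no rule for choosing among scores.

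The ingredients are open as well:

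- **Speech-in-noise** is "a set of tests with background noise/speech/babble, administered using appropriate programme through headphones" (section 5.2). Section 2 names two such tests, words in babble and words in speech noise.
- **PTA** is recorded for each ear by air and bone conduction, with no summary score defined.
- **Self-report** could be the modified Amsterdam Inventory ("a 28-point self-report questionnaire that assesses listening ability on 5 domains"), the SSQ ("contains 50 items and involves 3 hearing domains") or, less naturally, the Tinnitus Functional Index ("25-item self-report questionnaire"). ERSA, listed under quality of life, also measures the impact of hearing loss.

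Section 7.2.1 gives no sample size calculation and says that no test is accepted as a reference standard. The siderosis group is planned at 20–30.

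**The concern.** A claim that one test predicts better than another concerns a difference between two associations measured in the same people. Separate models do not estimate that difference. At n=20 a correlation is significant at the two-sided 5% level when it exceeds about 0.44, and at n=30 about 0.36. Observed correlations of 0.46 and 0.42 at n=20 would therefore be reported as one significant and one not, although they hardly differ.

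The freedom to choose adds to this. If several speech-in-noise scores are examined and the best is set against PTA, the side with more scores has the advantage even when all the tests are equally informative. At stake are the section 2 hypothesis and, so far as it rests on the same ranking, the tertiary answer. Objective 3 in section 4.1 wants results of this kind to identify outcome measures for diagnosis, monitoring and rehabilitation.

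**Working it through.** The plan gives no figure for this comparison, so there is none to reproduce. The inputs from the documents are n=20–30 and at least two speech-in-noise tests. The number of scores k, the number of PTA summaries m, the correlations and the picking of the best score are assumptions.

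**1. Ranking against PTA.** If k speech-in-noise scores and m PTA summaries are exchangeable and equally related to the criterion, each is equally likely to have the highest observed correlation. So P(a speech-in-noise score is highest) = k/(k+m), whatever n is. Simulation agrees.

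| k | m=1 | m=2 | m=3 |
|---|---|---|---|
| 2 | 67% | 50% | 40% |
| 3 | 75% | 60% | 50% |
| 4 | 80% | 67% | 57% |

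**2. Ranking against PTA plus speech-in-quiet.** Assume correlation 0.5 with the criterion and 0.6 between tests. The best single speech-in-noise score has a higher R-squared than the two-predictor model in 42%, 53% and 58% (k=2, 3, 4) at n=20, and in 40%, 50% and 57% at n=30. Unadjusted R-squared favours the model with two predictors. With adjusted R-squared the range is 48–68%.

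**3. Separate p-values.** Assume correlation 0.4 with the criterion for every test, 0.6 between tests, and one PTA average.

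| | a speech-in-noise score significant, PTA not | PTA significant, no speech-in-noise score |
|---|---|---|
| n=20, k=2 | 24% | 8% |
| n=20, k=3 | 29% | 5–6% |
| n=30, k=2 | 22% | 7% |
| n=30, k=3 | 25–26% | 4% |

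**4. Open criterion.** With three criteria correlated 0.7 (assumed), some speech-in-noise score is ahead of PTA on at least one of them in 84–88% of studies for k=2 and 91–93% for k=3. Even one score against one gives 70–74%, and PTA has that same chance, so an open criterion alone is not one-sided.

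**5. Pooling the three groups.** With group means differing on both measures, unit variance within groups and no association within any group, pooled r = v/(1+v), where v is the variance of the group means. Means (0, 2, 2) SD give v=0.889 and r=0.47. Means (0, 2, 1) give v=0.667 and r=0.40. The 2 SD is assumed. The inflation applies to any test that separates the groups, PTA included.

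**6. What a direct comparison can show.** For two dependent correlations both equal to r, with inter-test correlation q:

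Var(difference) = [2(1−r²)² − 2ψ]/n, with ψ = q(1−2r²) − ½r²(1−2r²−q²).

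- r=0.5, q=0.6: ψ = 0.3 − 0.0175 = 0.2825, and the numerator is 1.125 − 0.565 = 0.56. Half-width = 1.96√(0.56/20) = 0.33 at n=20, and 0.27 at n=30.
- r=0.4, q=0.6: ψ = 0.408 − 0.0256 = 0.3824, and the numerator is 1.4112 − 0.7648 = 0.6464. Half-width = 0.35 at n=20 (0.36 with n−1 as divisor), and 0.29 at n=30.

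With one score on each side, the Williams test at two-sided 5% rejects in 5.1% (n=20) and 4.8% (n=30) when the tests are equal. Its power for true correlations of 0.4 v 0.6 is 20% and 29%, and for 0.3 v 0.6 it is 39% and 57%. If the best of k scores were tested without adjustment, false findings in favour of speech-in-noise would rise from 2.5% to about 5% (k=2), 6–7% (k=3) and 8% (k=4).

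**The case against.** Much of the case on the other side stands.

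- **Both sides have choices.** PTA also has no defined summary. With two or three PTA summaries in play, the speech-in-noise advantage shrinks or disappears (step 1). The slash list of maskers is not firm evidence for three scores; two is the number that section 2 supports.
- **There are two comparators.** The hypothesis also names PTA with speech-in-quiet, and the k/(k+1) figure does not carry over to it (step 2).
- **The criterion is not wholly absent.** Section 2 names patient-reported difficulty as a class. What is missing is the instrument and the score.
- **The tertiary question can be read differently.** It may ask which tests separate the groups. The siderosis diagnosis is confirmed by a neurologist, independently of the hearing tests, and under that reading group differences are the signal. The self-report comparison comes from section 2.
- **The analysis text is brief.** It leaves model content open and provides for biostatistical advice, so reliance on separate p-values is an inference. But that advice does not itself fix the comparison, and the text as written offers no other basis for it.

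A reader might go further and infer that speech-in-noise would usually win whatever the truth, that pooling tilts the result towards it, or that the study will recommend it over PTA. The documents support none of these. The first needs unstated choices, pooling inflates PTA as well and is nowhere planned, and the stated aims favour an extended battery or a combination of tests.

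**Conclusion.** The point holds as a gap in the analysis: a comparative hypothesis has no comparative analysis, and the speech-in-noise score, PTA summary and criterion can all be chosen after the data are seen. Its size is conditional. Under equal merit, the chance that speech-in-noise ranks above PTA is 67–80% if only its own scores are selected from (k=2 to 4), and 40–67% if PTA summaries are too. Discordant p-values favour speech-in-noise over PTA by roughly 3 to 1 (k=2) or more, given one PTA average and the assumed correlations. That the answer moves so far with unstated choices is the reason to fix them. These percentages describe ranking or discordant significance; they are not error rates of a head-to-head test. The change is worth making because it is cheap and concerns a stated hypothesis; the gap does not undermine the study as a whole.

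**What to change.** In sections 4.2 and 5.5, before any analysis:

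1. Name one speech-in-noise score (for example words in babble, which section 2 already favours), one PTA summary (for example a better-ear four-frequency average) and one self-report criterion (for example the SSQ speech section).
2. For the siderosis claim, estimate within the siderosis group the difference between the two correlations with the criterion, with a Williams/Steiger or bootstrap 95% confidence interval. Working within group also removes the pooling problem.
3. For the second comparator, report the change in fit, with a bootstrap interval, when the speech-in-noise score is added to a model with PTA and speech-in-quiet.
4. Say 'better' only if the interval excludes zero; otherwise report the estimate as inconclusive.
5. Label other maskers, PTA summaries and questionnaires exploratory.
6. State whether the tertiary question means this comparison or separation of the groups, since the two need different analyses.

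The cost is wording and one or two short analyses, with no new data, visits or participants. The downside is that, at the half-widths and power in step 6, the claim becomes harder to make, so the result should be presented as an estimate with its interval.
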